3.1.3 Definition of non-tolerated dose

A dose will be considered non-tolerated, and dose escalation will cease, if ≥ 2 DLTs occur within a dose group (see Section 3.1.2).

3.1.4 Definition of maximum tolerated dose

When a non-tolerated dose is defined, dose escalation will be stopped and the MTD will be confirmed at the previous dose level below the non-tolerated dose, or a dose between the non-tolerated dose and last tolerated dose assessed may be investigated.

- If a dose between the non-tolerated dose and the last tolerated dose assessed is selected for investigation, then the dose escalation criteria detailed in Section 3.1.2 will apply
- When the non-tolerated dose is defined and the data on the dose below is based on data from <6 evaluable patients, then additional patients will be recruited at this lower dose to confirm that <2 DLTs have occurred in 6 evaluable patients treated at the MTD. If 5 evaluable patients in a given cohort have not experienced any DLTs, then further cohort expansion to confirm MTD is not required.

3.1.5 Definition of dose limiting toxicity

A DLT is defined as an AE or laboratory abnormality considered to be related to AZD8931, that commences anytime during the DLT evaluation period and meets any of the following criteria:

- Ophthalmological toxicity:
 - Symptomatic ocular surface lesion (epitheliopathy or erosion) with the following clinically significant criteria: >1 mm in diameter, <1 mm in diameter and clustered in a group of 10 or more, appearance of filaments or multiple (>2) small (<1 mm) areas or a large (>1 mm) area of negative fluorescein staining which cannot be attributed to another cause and which does not recover over a period of 3 days following detection of these findings.
- Haematological toxicity:
 - Any Common Terminology Criteria for AEs (CTCAE) grade 4 haematological toxicity of any duration
 - Febrile neutropenia (CTCAE grade ≥ 3 with temperature $\geq 38.5^{\circ}\text{C}$ which is unresponsive to antipyretics)
 - CTCAE grade ≥ 3 neutropenia requiring hospitalisation
 - CTCAE grade ≥ 3 thrombocytopenia associated with non-traumatic bleeding (but not applicable to patients on therapeutic anticoagulation)
- Clinical chemistry toxicity:
 - CTCAE \geq grade 3 hyperkalemia (ie, ≥ 6.0 mmol/L) which has been confirmed (by repeat sampling) and is considered to be drug related
 - CTCAE \geq grade 3 hyperglycemia (ie, ≥ 13.9 mmol/L), from fasting glucose, which has been confirmed (by repeat sampling) and is considered to be drug related
- Cardiovascular toxicity:
 - QTcF (Fridericia's correction) interval > 500 msec on two ECGs at least 30 minutes apart, that cannot be attributed to another cause
 - Symptomatic congestive cardiac failure (New York Heart Association [NYHA] class III/IV) and a drop in left ventricular ejection fraction (LVEF) which cannot be attributed to another cause²
 - A decrease in LVEF of $\geq 20\%$ to a level below the institution's lower limit of normal range
 - CTCAE ≥ 3 hypotension which cannot be attributed to another cause
- Other toxicities:

² Concomitant use of vasotonic drugs, adrenergic blockers, negative inotropic agents and anti hypertensives should be taken into consideration when assigning causality.

- Clinically significant rash that despite optimal treatment remains CTCAE grade ≥ 3 for 5 days or longer and that cannot be attributed to another cause.
 - CTCAE grade ≥ 3 urological toxicity which cannot be attributed to another cause
 - CTCAE grade ≥ 3 interstitial lung disease or pneumonitis which cannot be attributed to another cause
 - CTCAE grade ≥ 3 nausea, vomiting or diarrhoea, despite optimal anti-emetic or anti-diarrhoeal therapy, and which cannot be attributed to another cause
- Any other CTCAE grade ≥ 3 toxicity which, in the opinion of the investigator, is clinically significant and related to the study drug, with the exception of sub-optimally treated nausea, vomiting or diarrhoea

The National Cancer Institute (NCI) CTCAE version 3.0 will be used whenever applicable to characterise DLTs. However, pre defined stopping criteria will supersede the CTCAE criteria.

If patients present with a potential DLT, the patient should be promptly investigated to define the aetiology of the symptoms. The use of appropriate (ie non restricted) medications in prophylactic or therapeutic management of toxicities are permitted. In the case of suspected interstitial lung disease, specialist pulmonary consultation is strongly recommended.

The decision to interrupt dosing or to stop a patient from receiving further dosing will be taken by the principal investigator, in consultation with the study team, based on the clinical significance of the observed toxicity. If the toxicity is subsequently determined by the SMC to not be a DLT, this patient will be replaced.

The principal investigator, in consultation with the study physician, may request replacement of patients who develop DLTs which are attributed to confounding factors and concomitant medications started during the DLT assessment period. Confounding medications for the specific DLT will be prohibited for the new patient(s) recruited to that dose group.

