3.4.4 Method of assigning subjects to treatment groups

Informed consent will be obtained at screening and each patient will be identified with a unique screening number starting with E# (incorporating centre identification). This number will be retained regardless of whether they subsequently fulfil the eligibility criteria.

Patients will be assigned patient numbers strictly sequentially as patients become eligible for inclusion. If a patient discontinues from the study the patient number will not be re-used and the patient will not be allowed to re-enter the study.

Patients may be replaced if they are withdrawn without meeting all the criteria for a DLT (see Section 3.1.2), or withdrawn due to a DLT that is attributed to taking confounding medications (see Section 3.1.5), or if they are enrolled in error (see Section 3.3.5.4), or if they are non-evaluable (see Section 6.4.3).

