6.4.3 Description of analysis sets

Three patient analysis sets will be used as defined in Table 4; the safety set, the dose escalation evaluable set and the PK evaluable set. The primary analysis set will be the dose escalation evaluable set.

Table 4 **Definition of analysis sets**

Analysis set	Definition
Safety set	This population comprises all patients entered into the study who received at least one dose of AZD8931
Dose escalation evaluable set*	All patients in the safety set who have either experienced a DLT, or received at least 80% of planned doses of AZD8931 and who had all safety assessments completed during the DLT evaluation period
PK evaluable set	All patients in the safety set who have Day D1 PK data and/or have Day R14 PK data (and have received all doses during the day before Day R14)

*The SMC decide evaluability in the absence of appropriate assessments

Rules for identification of significant protocol violations will be given in the SAP. If a substantial number of patients are deemed to be protocol violators a separate ‘per-protocol’ analysis set will be determined, prior to analysis, which will exclude these patients.

6.4.4 **Methods of statistical analyses**

6.4.4.1 **Pharmacokinetic data**

The PK analysis is described in Section 6.1.1. The PK endpoints will be listed for individual subjects and summarised by dose level.

6.4.5 **Determination of sample size**

No formal sample size calculations were performed since the study follows a 3+3 dose group dose escalation design (see Section 3.1.2).

6.5 **Interim analyses (Not applicable)**

No interim analyses are planned.

6.6 **Data monitoring committee**

Working rules of the SMC are described in the SMC charter.

The SMC will comprise:

- The principal investigators of all sites
- The AstraZeneca physician
- The Medical Monitor.

In each case at least one deputy may be nominated.

On a case-by-case basis, the SMC may seek advice from further experts, including qualified representatives of AstraZeneca/

Following completion of the DLT period by ≥ 3 evaluable patients, the SMC will review all available data and decide upon dose progression. Further ‘ad-hoc’ meetings of the SMC may be convened, if required.

The safety review of data from each dose group will lead to one of 4 possible outcomes:

- Escalate to a higher dose
- Repeat dose level in further patients to obtain 6 evaluable patients at that dose level

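### A patient who already has a DLT may be replaced for confounding, while Table 4 keeps that patient in the evaluable set and no section says whether the DLT still counts toward the limit of two

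*Protocol*

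**What the plan says.** **Definition.** Protocol Section 3.1.5 opens with "A DLT is defined as an AE or laboratory abnormality considered to be related to AZD8931, that commences anytime during the DLT evaluation period". Relatedness is therefore part of every DLT. Some criteria go further; the QTcF criterion, for example, reads "msec on two ECGs at least 30 minutes apart, that cannot be attributed to another cause". Others add nothing on cause; one haematological criterion is any grade 4 "haematological toxicity of any duration".

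**Replacement of DLT patients.** Later in Section 3.1.5 the principal investigator, once the study physician has been consulted, "may request replacement of patients who develop DLTs which are attributed to confounding factors and concomitant medications started during the DLT assessment period". For the replacement, "Confounding medications for the specific DLT will be prohibited for the new patient(s) recruited to that dose group". Section 3.4.4 lists among the replaceable patients those "withdrawn due to a DLT that is attributed to taking confounding medications".

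**Separate route for non-DLTs.** The paragraph before the request rule in Section 3.1.5 already provides that a patient is replaced if the SMC finds that the toxicity was not a DLT.

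**Evaluability.** Table 4 (Section 6.4.3) defines the dose escalation evaluable set as "All patients in the safety set who have either experienced a DLT, or received at least 80% of planned doses of AZD8931" with all safety assessments completed. There is no exception for a confounded DLT. The footnote gives the SMC a say on evaluability only where assessments are missing. Section 3.4.3 agrees with Table 4: a dose reduction in the DLT period ends evaluability unless a DLT has already occurred.

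**Decision rule.** Sections 3.1.2 and 3.1.3 declare a dose non-tolerated at two or more DLTs. Section 3.1.2 closes a cohort at six evaluable patients.

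**The concern.** Causality is judged when an event is classified as a DLT. The request rule then allows a second judgement on cause for events that have passed the first. The request comes from the site where the event occurred, after the outcome is known, and the protocol names no approver, no deadline and no record.

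Table 4 says that such a patient is evaluable; Sections 3.1.5 and 3.4.4 say that the patient may be replaced. The two cannot both hold in a cohort capped at six. Section 3.3.5.4 (patients enrolled in error are non-evaluable for MTD) and Section 3.4.6 (patients given listed concomitant medication could be non-evaluable) raise the same conflict, because neither says what happens if the patient has had a DLT.

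At stake is the count that decides escalation and the MTD. With a limit of two in at most six patients, one DLT counted or not counted can settle the decision. Table 4's set is also the declared primary analysis set.

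**Working it through.** **1. Is cause already settled in the definition?** Section 3.1.5 lists 16 criteria: 1 ocular, 4 haematological, 2 clinical chemistry, 4 cardiovascular and 5 other.

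- 8 expressly rule out another cause: ocular, QTcF, cardiac failure, hypotension, rash, urological, interstitial lung disease, and nausea/vomiting/diarrhoea.
- 3 repeat drug-relatedness only: hyperkalaemia, hyperglycaemia, and any other grade 3 or higher toxicity.
- 5 rest on the opening requirement of relatedness: the four haematological criteria and the LVEF decrease.

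So 8 of 16 exclude other causes in words, and all 16 require relatedness. Under Appendix B, relatedness fails where another cause is more likely.

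**2. Does replacement take the DLT out of the count?** This is not stated. Two points favour that reading.

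- With six evaluable patients, a DLT patient who stays evaluable leaves no place for a replacement.
- With fewer than six, Section 3.1.2 already requires more patients after one DLT. Replacement that left the DLT counted would add little to that.

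**3. Two readings of one cohort.** Take six evaluable patients with two DLTs, one attributed to a newly started medication.

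- Table 4 reading: 2 of 6, non-tolerated, escalation stops.
- Replacement reading: the count becomes 1 of 6 if the new patient has no DLT, and stays at 2 if the new patient has one. With true DLT rate p, the chance of falling below 2 is 1 − p: 67% at p = 0.33 and 50% at p = 0.50.

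**4. Illustrative size.** The protocol's only size figure, about 30 evaluable patients, is 5 groups × 6 = 30. There is no formal calculation, and this point does not depend on that figure. The true rate p and the share r of DLT patients replaced are assumptions; the protocol gives neither.

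Each replacement is taken to have the same risk p, and a DLT in a replacement may itself be replaced with probability r. The effective rate is then

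p′ = p(1 − r) / (1 − pr).

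On the 3-then-6 path, with 1 of 6 accepted:

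P(non-tolerated) = P(≥2 of 3) + P(1 of 3) × P(≥1 of next 3).

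At p = 0.33 and r = 0: 0.2548 + 0.4444 × 0.6992 = 0.566.

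At p = 0.33, p′ is 0.297/0.967 = 0.307 for r = 0.10, 0.2475/0.9175 = 0.270 for r = 0.25, and 0.165/0.835 = 0.198 for r = 0.50.

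P(non-tolerated), 3-then-6 path:

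| True rate p | r = 0 | r = 0.10 | r = 0.25 | r = 0.50 |
|---|---|---|---|---|
| 0.20 | 29.1% | 25.6% | 20.2% | 11.3% |
| 0.33 | 56.6% | 52.0% | 44.3% | 28.6% |
| 0.50 | 82.8% | 79.7% | 73.5% | 57.2% |

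If six are dosed at once, which the protocol allows, the p = 0.33 row is 64.2, 59.5, 51.2 and 33.9%.

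**The case against.** **An event can be related and still confounded.** Appendix B sets a low bar for relatedness: one supporting factor can suffice, and ambiguous cases count as possible. Appendix F lists inhibitors that may raise AZD8931 exposure more than threefold. A toxicity on such a drug is related to AZD8931 yet says little about the assigned dose. This stands. It means that the table overstates the bias wherever the replaced events truly are uninformative. It does not explain why such events need a second route with no named decision-maker, when the SMC's finding of no DLT already leads to replacement.

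**A reader might infer that counted DLTs are removed and the MTD is raised.** The documents do not say so. Section 3.1.5 speaks of replacement only. Section 3.1.3 counts DLTs that occur within a dose group, and Table 4 keeps the patient. Read strictly, the DLT stays counted. The finding is that the text supports both readings.

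**A reader might infer that the investigator can act alone, without the SMC.** The text gives a right to request. Section 6.6 requires an SMC consensus on dose progression, and the SMC charter is not at hand. What stands is that the protocol names no one who grants the request. The SMC also includes the site principal investigators.

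**A reader might infer that replacement for confounding reaches only DLT patients.** Section 3.4.6 allows replacement for listed medication with or without a DLT. The one-way effect belongs to the DLT request route alone.

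**A reader might see a clash between Section 3.4.4, which speaks of meeting all DLT criteria, and Section 3.1.5, where any one suffices.** The former can mean relatedness, onset in the period and a listed criterion together. No change is needed there.

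**Conclusion.** The conflict is real and sits in the rule that drives escalation. Sections 3.1.5 and 3.4.4 allow replacement of a patient whose event is already a DLT; Table 4 keeps that patient evaluable; and nothing says who decides, when, or whether the DLT counts toward two. Sections 3.3.5.4 and 3.4.6 conflict with Table 4 in the same way. Sections 3.1.5 and 3.4.4 also differ in scope: the first covers confounding factors and medications, the second only medications and only withdrawn patients.

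That the DLT leaves the count is an inference, though the natural one. If it holds, each use of the request route lowers the count by one or leaves it unchanged. The size depends wholly on the assumed p and r: at p = 0.33, modest at r = 0.10 (4.6 percentage points) and large at r = 0.50 (28.0 points). These figures show direction and scale and do not predict what the trial will do.

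**What to change.** Reconcile Sections 3.1.5, 3.4.4, 3.3.5.4 and 3.4.6 with Table 4 through one decision point:

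- Before each escalation decision the SMC classifies every candidate event as DLT or not DLT, and minutes the reason, including any confounding.
- An event classified as not a DLT follows the replacement route already in Section 3.1.5.
- A patient classified as having a DLT stays in the dose escalation evaluable set and counts toward the limit of two. The separate request route in Sections 3.1.5 and 3.4.4 for classified DLTs is removed.
- Sections 3.3.5.4 and 3.4.6 state how they apply once a DLT has been classified, in agreement with Table 4.

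The medication restriction that Section 3.1.5 places on replacement patients makes conditions differ within a dose group. The passages should be reconciled on this too; which restriction should apply is a clinical matter and is left open here.

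The cost is protocol wording, with no new data or patients planned. The downside is small: an occasional partly confounded DLT stays in the count, with the confounding on record in the SMC minutes.

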3.1.6 Study flow chart and study plan

Figure 2 Study flow chart

3 to 6 patients	Single dose	4-day observation period	Twice daily dosing for 21 days	Data collection /review	SMC review	Single dose	4-day observation period	Twice daily dosing for 21 days...
Day	D1		D5 to 7			(1)		
Repeat dosing day			R1.....R21					

(1) New dose group (increased dose, same dose, decreased dose) depending on result of SMC meeting to discuss previous dose cohort of 3 to 6 evaluable patients (see Section 6.6).

Abbreviations: SMC: Safety Monitoring Committee. Shading: AZD8931 treatment.

Table 1 Study plan

Assessments	Screening	DLT Evaluation Period ^a									Premature discontinuation	Continuation beyond R21 ^a	Post-study follow-up
		Single dose											
Day (h = hours)	D-21 to D0	D1	D2 (24 h)	D3 (48 h)	D4 (72 h)	D5 to D7						Every 3 weeks	7 days after last dose
Repeat dosing (R) day (d=day)						R1	R3	R7 ±1d	R14 ±1d	R21 ±1d	≤2d	±3d	±1d
Informed consent (main study, genetics [optional], proapoptotic biomarkers [optional])	x												
Inclusion/exclusion criteria	x												
Tumour TNM stage at diagnosis and at study entry (and ErbB2 status, if available)	x												
Tumour assessment (RECIST)	x ^b										x ^c	x ^d	
Chest X-ray	x												
Demographics	x												
Medical/surgical history	x												
Previous anticancer therapy, including surgery	x												
Urine pregnancy test	x												
Administer AZD8931		Single dose ^e				Twice daily for 21 days ^e						Twice daily ^e	
Physical examination	x										x		x
Dermatological examinations ^f	x									x	x		x ^g

Table 1 Study plan

Assessments	Screening	DLT Evaluation Period ^a									Premature discontinuation	Continuation beyond R21 ^a	Post-study follow-up
		Single dose											
Day (h = hours)	D-21 to D0	D1	D2 (24 h)	D3 (48 h)	D4 (72 h)	D5 to D7						Every 3 weeks	7 days after last dose
Repeat dosing (R) day (d=day)						R1	R3	R7 ±1d	R14 ±1d	R21 ±1d	≤2d	±3d	±1d
Ophthalmological assessments	x									x	x	x ^h	x ^g
Echocardiography	x									x	x	x ⁱ	x ^g
12-lead Electrocardiogram ^j	x	x ^k	x	x	x	x	x ^l	x ^l	x ^k	x	x	x	x
Vital signs (heart rate, blood pressure)	x	x ^k	x	x	x	x	x ^l	x ^l	x ^k	x	x	x	x
Blood sample for AZD8931 pharmacokinetic (PK) analysis		x ^k	x	x	x		x ^l	x ^l	x ^k				
Blood sample for clinical chemistry, haematology, coagulation parameters	x	x ^{l,m}	x	x	x	x ^l	x ^l	x ^l	x ^{l,m}	x ^l	x	x	x
Blood samples for proapoptotic biomarkers (optional)		x ^{l,n}					x ^l	x ^l	x ^l	x ^l	x	x ^l	x ^g
Blood sample for pharmacogenetics (optional)		x ^o											
Urine sample for urinalysis	x	x ^l	x	x	x	x	x	x	x	x	x	x	x
Patient diary (including times study drug taken on PK days, and survey of ophthalmological [weekly] and other symptoms)						x ^p	x ^p	x ^p	x ^p	x ^p		x ^p	

Table 1 Study plan

Assessments	Screening	DLT Evaluation Period ^a									Premature discontinuation	Continuation beyond R21 ^a	Post-study follow-up
		Single dose											
Day (h = hours)	D-21 to D0	D1	D2 (24 h)	D3 (48 h)	D4 (72 h)	D5 to D7						Every 3 weeks	7 days after last dose
Repeat dosing (R) day (d=day)						R1	R3	R7 ±1d	R14 ±1d	R21 ±1d	≤2d	±3d	±1d
Concomitant medications	x	x	x	x	x	x	x	x	x	x	x	x	x
Adverse events	x	x	x	x	x	x	x	x	x	x	x	x	x

TNM = Tumour, Node, Metastases; RECIST = Response Evaluation Criteria In Solid Tumours; HbA1c = glycosylated haemoglobin

Notes to study plan

^a Treatment should be extended beyond day R21 if, in the investigator's opinion, the patient is receiving or may receive some benefit from therapy is free from intolerable toxicity and has not met a discontinuation criterion (see Section 3.3.5.1).

^b Baseline radiological tumour assessments should be performed no more than 4 weeks before the start of study treatment, but should be as close as possible to the start of study treatment.

^c Where possible and appropriate.

^d Every 6 weeks (±7 days), relative to day R1, until objective disease progression, study drug discontinuation, withdrawal of informed consent or death (whichever is soonest).

^e No food is allowed from 2 hours before to 2 hours after study drug dosing.

^f Full examination at screening (see Section 4.4.4). Full examination at other visits only if clinically significant abnormalities are observed. Brief symptom-directed examinations, or follow-up of existing abnormalities, should be performed at study visits, as appropriate.

^g Only if not performed at day R21 (or premature discontinuation visit).

^h Full ophthalmological assessment will be done at screening. Thereafter it will be done at premature discontinuation or day R21, whichever is earliest. Beyond day R21, questionnaire survey will be done every cycle or at discontinuation, with full examination only if indicated in accordance with the protocol.

ⁱ Every 9 weeks for 3 times, then every 18 weeks.

^j 12-lead electrocardiogram (ECG) after 10 minutes rest in the supine position. The patient should be examined using the same machine throughout the study. Digital ECGs for QTc interval analysis (days D1 and R14) must be in triplicate (one after another). Paper read-outs are sufficient for other assessments.

^k At pre-dose and at 1, 2, 4, 6, 8 and 12 hours post-dose (days D1 and R14).

^l Pre-dose.

Amended Clinical Study Protocol
Drug Substance AZD8931
Study Code **D0102C00002**
Edition Number 3
Date

- ^m Glucose and potassium only at 6 hours post-dose (days D1 and R14).
- ⁿ At 8 hours post-dose.
- ^o After confirmation of eligibility.
- ^p Daily.
- ^q The DLT evaluation period starts from the first administration of AZD8931 and continues until the completion of all assessments prior to cycle 2 see Section [3.1.2](#) for further information

3.2 Rationale and risk/benefit assessment

AZD8931 is in development for the treatment of patients with solid malignancies. Modulation of the EGF and ErbB2 receptors has been shown to provide clinical benefit for other agents. Non-clinical testing has indicated that patients with Erb family-driven solid tumours may benefit from treatment with AZD8931. However, at present there are no data available from exposure of patients to AZD8931, consequently there are no clinical benefit data available yet.

The proposed initial dose (ie, 40 mg twice daily) is considered unlikely to elicit significant target related pharmacological or clinical effects. Whilst patients are unlikely to gain therapeutic benefit, participation in the study will provide information on the safety and tolerability profile of AZD8931, together with PK and pharmacodynamic data, which will support the future clinical development of AZD8931 for the treatment of cancer and potentially meeting the unmet medical need in future cancer patient populations.

In order to provide a risk/benefit assessment for this study, detailed rationales for the choice of patient population, doses and design (including inclusion/exclusion, and stopping criteria) of this study are provided below.

